9.6.2 Statistical Methods for Safety Analyses

Safety will be assessed by statistical and clinical review of all safety data collected throughout the study. All participants who are vaccinated and who have safety follow-up data will be included in the safety analyses and summaries. To provide an overall assessment, safety measures that occurred in the pre-defined time interval during the study will be summarized, such as the incidence of

1. any adverse events;
2. any injection-site adverse events;
3. any systemic adverse events;

4. any serious adverse events;
5. any vaccination-related adverse events;
6. any vaccination-related serious adverse events;
7. conditions of particular attention (CPA^{*});
8. pregnancy outcomes;
9. new medical conditions.

^{*}: More details about CPA will be provided in the sSAP.

Stage I (Day 1 to Visit 10):

Summary statistics, counts and percentages and 95% confidence interval will be provided by age groups: (1) 9- to 19-year-old group; (2) 20- to 26-year-old group; and (3) 27- to 45-year-old group which are summarized in [Table 5](#).

Table 5 Analysis Strategy for Safety Parameters

Safety Endpoint	Within Group 95% CI	Descriptive Statistics
Injection-site adverse events prompted for on the VRC occurring Day 1 to Day 8 following any vaccination	×	×
Solicited systemic AE (elevated axillary temperature ($\geq 37.1^{\circ}\text{C}$)) from Day 1 through Day 8 following any vaccination	×	×
Injection-site adverse events not prompted for on the VRC occurring Day 1 to Day 8 following any vaccination in $\geq 1\%$ of participants in any age group	×	×
Systemic adverse events in $\geq 1\%$ of participants in any age group within 30 days following any vaccination	×	×
Serious adverse events at any time during study	×	×
Vaccination-related serious adverse events observed at any time during the study	×	×
Injection-site severe or more adverse events (by CFDA grading scale) occurring Day 1 to Day 8 following any vaccination	×	×
Injection-site severe adverse events (by Merck grading scale) occurring Day 1 to Day 8 following any vaccination	×	×
Systemic severe or more adverse events (by CFDA grading scale) within 30 days following any vaccination	×	×
Systemic severe adverse events (by Merck grading scale) within 30 days following any vaccination	×	×
Conditions of particular attention	×	×
All injection-site adverse events occurring Day 1 to Day 8 following any vaccination		×
All systemic adverse events within 30 days following any vaccination		×

Both Sponsor's criteria (Section 10.3 – Appendix 3) and CFDA's criteria (Section 10.4 - Appendix 4) will be applied to assess the intensity/toxicity of adverse events by investigator. The incidence of greatest intensity/toxicity based on the two criteria will be tabulated for injection-site AEs and systemic AEs.

All pregnancy outcomes and infant SAEs will be summarized.

Stage II (post-Visit 10 to Visit 15):

Summary statistics, including counts and proportions of participants with SAEs during the entire period of Stage II will be summarized for 9-19 years old participants.

In addition, all pregnancy outcomes and infants SAEs will be summarized.

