8.3.1 Vaccination Report Card and Patient Reported Outcome

All participants will receive a VRC at each study vaccination visit (Visit 1, Visit 4, and Visit 8).

Using the VRC, participant or participant's legally acceptable representative will be asked to record the following safety information: axillary temperature in the evening after each study vaccination and daily, at the same time of day whenever possible, for 7 days after each study vaccination; solicited injection-site AEs (injection-site redness, swelling, induration, and pain) from Day 1 through Day 8 after each study vaccination; any AEs from Day 1 through Day 31 after each study vaccination. Participant or participant's legally acceptable representative will be asked to record concomitant medications and concomitant vaccinations for 15 days following each study vaccination on VRC. Medications taken by participants due to AEs during Day 16 through Day 31 after each study vaccination will also be collected on VRC.

VRCs will be returned for review on Day 9 (i.e. Visit 2, Visit 5, and Visit 9) and Day 32 (i.e. Visit 3, Visit 7, and Visit 10) after each study vaccination, respectively. The first 25 participants enrolled in the 9-15 years old group will have an additional VRC return visit (Visit 6) to collect the safety data through Day 15 following the 2nd dose.

Except Visit 10 (1 month post Dose 3) at which visit blood samples will be collected, the purpose of other VRC return visits is to review the VRCs, so out of windows will not be considered as protocol deviation for Visit 2, Visit 3, Visit 5, Visit 6, Visit 7, and Visit 9. However, Visit 10 sample collection out of windows will be considered as a protocol deviation.

Telephone contacts will be done around every week between Visit 2 and Visit 3, Visit 5 and Visit 7 (telephone contacts will be done after Visit 6 for the first 25 participants in the 9-15 years old group), Visit 9 and Visit 10 until the VRCs are returned to remind the participants to record the VRC and answer any questions related to VRC.

SAEs, cancers, overdoses, pregnancy events, lactation events, and infant SAEs will be collected during the entire study period as instructed in the Section 8.4.

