8.4 Adverse Events (AEs), Serious Adverse Events (SAEs), and Other Reportable Safety Events

The definitions of an AE or SAE, as well as the method of recording, evaluating, and assessing causality of AE and SAE and the procedures for completing and transmitting AE, SAE, and other reportable safety event reports can be found in Section 10.3 - Appendix 3.

AE, SAEs, and other reportable safety events will be reported by the participant (or, when appropriate, by a caregiver, surrogate, or the participant's legally authorized representative).

The investigator and any designees are responsible for detecting, documenting, and reporting events that meet the definition of an AE or SAE as well as other reportable safety events. Investigators remain responsible for following up AE, SAEs, and other reportable safety events for outcome according to Section 8.4.3.

The investigator, who is a qualified physician, will assess events that meet the definition of an AE or SAE as well as other reportable safety events with respect to seriousness, intensity/toxicity and causality.

8.4.1 Time Period and Frequency for Collecting AE, SAE, and Other Reportable Safety Event Information

All AEs, SAEs and other reportable safety events that occur after the consent form is signed but before allocation/randomization must be reported by the investigator if they cause the participant to be excluded from the study, or are the result of a protocol-specified intervention, including but not limited to washout or discontinuation of usual therapy, diet, placebo treatment or a procedure.

From the time of allocation/randomization through 30 days following the first vaccination(s) and from the time of any subsequent vaccination(s) through 30 days thereafter, all AEs, SAEs and other reportable safety events must be reported by the investigator.

SAEs (regardless of causality) at any time outside of the time period specified in the previous paragraph also must be reported immediately to the Sponsor. Other reportable safety events (cancer, pregnancy, breastfeeding exposure, and overdose) at any time outside of the time period specified in the previous paragraph should also be reported to the Sponsor. In addition, SAEs of infants born to participants who received the study vaccine or who were breastfed during the study are reportable for the entire study period.

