8.4.2 Method of Detecting AEs, SAEs, and Other Reportable Safety Events

A VRC will be used by the participant to document any AEs within 30 days (Days 1-31) following each study vaccination.

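### Every injection-site row of Table 5 stops at Day 8, so a non-serious injection-site AE starting on Days 9 to 31 enters no injection-site or severity row of that table

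*Combined protocol and SAP*

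**What the plan says.** **Collection.** Section 8.3.1 sets two windows on the vaccination report card. The prompted local items have the short one: "solicited injection-site AEs (injection-site redness, swelling, induration, and pain) from Day 1 through Day 8 after each study vaccination". Everything else has the long one: "any AEs from Day 1 through Day 31 after each study vaccination". Section 8.4.2 repeats the long window without a split by type: "A VRC will be used by the participant to document any AEs within 30 days (Days 1-31) following each study vaccination". Section 8.4.1 puts the same duty on the investigator after each later dose: "through 30 days thereafter, all AEs, SAEs and other reportable safety events must be reported by the investigator". None of these leaves out injection-site events.

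**Tabulation.** Table 5 (Section 9.6.2) has five injection-site rows:

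- prompted events: "Injection-site adverse events prompted for on the VRC occurring Day 1 to Day 8 following any vaccination"
- unprompted events, listed only if they reach 1% in some age group: "Injection-site adverse events not prompted for on the VRC occurring Day 1 to Day 8 following any vaccination"
- severe or worse on the CFDA scale, Day 1 to Day 8
- severe on the Sponsor's scale: "Injection-site severe adverse events (by Merck grading scale) occurring Day 1 to Day 8 following any vaccination"
- the total: "All injection-site adverse events occurring Day 1 to Day 8 following any vaccination"

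The systemic rows for common events, for severe events on each scale and for all events run to 30 days. SAEs are counted at any time.

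**Outside the table.** Section 9.6.2 opens with a list of overall summaries. It includes any AE, any injection-site AE and any vaccination-related AE, over a pre-defined interval that is not stated there. After Table 5 it promises a tabulation of greatest intensity on both scales for injection-site and systemic AEs, again with no day window.

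**The concern.** A Day 8 limit suits the prompted row, because prompting ends then. The unprompted, severe and total rows draw on events that are collected to Day 31, and nothing in the text explains why those rows stop 23 days sooner. Systemic events are treated differently in the same table: elevated temperature has a Day 1 to 8 prompted row, and systemic AEs also have 30-day rows for incidence and severity. Injection-site events have no second window.

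What is at stake is completeness of the local-reaction and severity reporting. Safety is a Stage I secondary objective, and Stage I is meant to support extending the indication to ages 9 to 15 and 27 to 45. A reader who looks to Table 5 for all or for severe injection-site AEs would not find a late one there unless it also qualified for an SAE row or as a condition of particular attention. Appendix 3 is explicit that severe does not mean serious.

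**Working it through.** No power, alpha or sample-size figure bears on this, so there is no stated figure to reproduce. The check compares windows.

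**Inputs.** Collection is Days 1 to 31 per dose (Sections 8.3.1, 8.4.1, 8.4.2). The Table 5 injection-site rows cover Days 1 to 8 (Section 9.6.2). There are three doses. I read an event's day as its day of onset.

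**Days collected but outside every injection-site row.**

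- Per dose: 31 − 8 = 23 days (Days 9 to 31); 23/31 = 74%.
- Over three doses: 3 × 23 = 69 of 3 × 31 = 93 days.

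This is a share of calendar days, not of events.

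**Where a non-serious injection-site AE starting on Days 9 to 31 can go.**

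| Output in Section 9.6.2 | Window and scope | Takes the event? |
|---|---|---|
| Five injection-site rows of Table 5, two of them severity rows | Days 1 to 8 | No (0 of 5) |
| Two systemic severity rows of Table 5 | 30 days, systemic only | No |
| Common and all systemic AE rows of Table 5 | 30 days, systemic only | No |
| Conditions of particular attention | Potentially autoimmune events only (Section 9.4.2) | Only if so classified |
| SAE rows | Any time, serious only | No |
| Any AE (overall list) | Interval not stated; all types | Can |
| Any vaccination-related AE (overall list) | Interval not stated; related only | Can, if related |
| Any injection-site AE (overall list) | Interval not stated | Not determined |
| Greatest-intensity tabulation | No window stated | Not determined |

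Severity rows in Table 5: two injection-site rows that stop at Day 8 plus two systemic rows, so 0 of 4.

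The new-medical-conditions summary is no substitute. Section 8.3.1 reserves it for events outside the 31-day period after vaccination.

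**Is later grading possible?** Appendix 3 evaluates redness and swelling by maximum size within 7 days. Its general mild, moderate and severe definitions carry no day limit, and neither do the CFDA local-reaction grades in Table 11. A late local event can therefore be graded on both scales.

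**Number of participants.** The documents give no rate of late-onset injection-site AEs. For scale only, an assumed 0.1% of 1990 is about 2 participants and an assumed 1% is about 20, at any intensity. Nothing in the documents supports a value in that range. Neither count can be carried to the severity rows, which take only the unknown severe fraction.

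**The case against.** The best defence is that the window is deliberate and that the events have other outlets.

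**Deliberate.** Section 9.4.2 names solicited injection-site AEs on Days 1 to 8, systemic AEs on Days 1 to 31 and SAEs at any time as key endpoints. The Stage I safety objective names only solicited events and SAEs. No stated objective or key endpoint concerns an unsolicited local event after Day 8, and safety is descriptive. This stands as a limit on importance. It does not explain the unprompted, severe and total rows, which already go beyond solicited events and are cut at Day 8 all the same.

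**Other outlets.** A reader might infer that a late reaction surfaces only in the undifferentiated count of any AE, or that a severe one is reported as severe nowhere. The documents do not support that. A related event also enters the vaccination-related count. The any-injection-site line and the greatest-intensity tabulation state no window and might include it. They do not establish the opposite either: the only injection-site window that Section 9 states is Day 1 to 8.

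**Labels.** A reader might call the Table 5 rates undercounts. They are not: each row states its window and is correct for it.

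**Low yield.** The unprompted row lists only events reaching 1% of an age group, which is 7 participants in a group of 650 or 690 (1% is 6.5 or 6.9). Extending that row would probably add little. This stands, and the fix leaves that row alone.

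**Conclusion.** The point holds as a statement about the rows of Table 5: a non-serious injection-site AE starting on Days 9 to 31 enters 0 of 5 injection-site rows and 0 of 4 severity rows, although it is collected and reportable. The uncovered stretch is 23 of 31 days per dose.

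It does not follow that 74% of injection-site events are missed, since onset need not be spread evenly over the days. Nor does it follow that late events drop out of the analysis. The number affected is unknown and probably small. No hypothesis, alpha level, power figure or success criterion is touched. This is a minor gap in descriptive safety reporting, together with two summaries whose windows need to be stated. The conclusion rests on reading the rows by day of onset.

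**What to change.** 1. Keep all existing Day 1 to 8 rows, so that those rates remain available for their labelled window.
2. Add three parallel descriptive rows to Table 5, for Days 9 to 31 or Days 1 to 31: all injection-site AEs; injection-site AEs severe or worse on the CFDA scale; and injection-site AEs severe on the Sponsor's scale.
3. State Day 1 to 31 as the window for the overall any-injection-site-AE line and for the injection-site part of the greatest-intensity tabulation.

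The cost is a few extra table rows with sparse counts. No new data, visits or participants are needed, because the report card already runs to Day 31. The opening of Section 9 allows changes to non-confirmatory analyses before final database lock to be documented in the supplemental SAP, so the change can be made there.

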9.6.3 Summaries of Baseline Characteristics, Demographics, and other Analyses

Baseline characteristics, demographic variables, medical history, prior and concomitant therapies of females 9 to 45 years of age will be summarized using descriptive statistics or categorical tables. No statistical hypothesis tests will be performed on these characteristics.

The number and percentage of participants screened, allocated, the primary reasons for screening failure, and the primary reason for discontinuation will be displayed.

New medical conditions will be collected during the entire period of the study. However, the data of new medication conditions will be separately summarized for Stage I and Stage II.

9.7 Interim Analyses

One interim analysis will be performed in this study to evaluate the safety of the 9vHPV vaccine from Dose 1 through Day 15 following Dose 2 in a subset of 25 participants aged 9-15 years. The safety data will be reviewed by a DMC. If the safety data are judged to be acceptable in the opinion of the DMC, then these 25 participants will receive the 3rd dose at Visit 8 and the enrollment will be initiated to the rest of participants in the 9-15 years old group. Available safety data from the 16-26 years old group will be provided along with the subset of 25 participants in the 9-15 years old group in order for the DMC to complete their safety evaluation.

This study is composed of two stages. Database will be locked and analyses will be conducted after completion of each stage. A full CSR will be generated for Stage I and a supplemental statistical report will be generated for Stage II.

9.8 Multiplicity

Figure 2 shows the multiplicity strategy for the study.

[figure not shown]

Figure 2 Multiple Strategies to Control Overall Type One Error Rate

For the dual-primary hypotheses (H1 and H2), Bonferroni method is used to control overall one-sided type I error at level of 0.025. Each of the dual-primary hypotheses has a 0.0125 one-sided type I error. The study would be successful if either H1 or H2 are met. If H1 is not met then no further testing (H3, H4) will be completed.

Fix sequence testing strategy is used to control multiplicity between dual-primary hypothesis (H1) and secondary hypotheses (H3 and H4). The testing order is as follows: H1 (GMT, 9-19yr vs.20-26yr) will be tested firstly and if H1 wins H3 (seroconversion percentages, 9-19yr vs. 20-26yr) will then be tested; if H3 wins H4 (GMT, 9-15yr vs. 20-26yr) will be tested. Each one will be tested at a level of 0.0125. If anyone failed to reject null the subsequent ones would not be tested.

Furthermore, success is required on all 9 HPV types for hypotheses testing GMT and seroconversion percentages, so no multiplicity adjustment is needed to account for the multiple HPV types.

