9.9 Sample Size and Power Calculations

9.9.1 Sample Size and Power for Immunogenicity

Approximately 1990 participants will be enrolled in the study with the following allocated sample sizes for each age group as: 690 participants in 9-19yr age group (460 in 9-15yr and 230 in 16-19yr), 650 participants in 20-26yr age group, and 650 participants in 27-45yr age group. The overall power to claim the study success based on the dual-primary hypotheses is >0.999.

Two dual-primary hypotheses (H1 and H2) and two secondary hypotheses (H3 and H4) are considered when determine overall sample size and the sample sizes allocated to each age group. The calculations are based on the following assumptions:

- 1) HPV Types 6, 11, 16, 18, 31, 33, 45, 52, 58 responses are identical in 9-15yr, 9-19yr, and 20-26yr age groups;

- 2) HPV Types 6, 11, 16, 18, 31, 33, 45, 52, 58 seroconversion percentages are identical in 9-19yr, 20-26yr, and 27-45yr age groups;
- 3) The overall percentages of participants not eligible for per-protocol analyses for each HPV type are 15% in 9-15yr age group, 9-19yr age group, 30% in 20-26yr and 27-45yr age groups which are calculated based on:
 - percentage of the participants are initially seropositive to each HPV type
 - expected attrition rate through 1 month post Dose 3 (Visit 10)
 - expected percentage of participants excluded due to vaccinations or serology samples out of range
- 4) The standard deviations of the natural logarithm of the Visit 10 titers are no more than 1.2 for each HPV type when expressed as mMU/mL, the unitage used in previous HPV vaccine studies;
- 5) Regarding to the dual-primary hypotheses (H1 and H2), Type I error will be controlled by Bonferroni Method, i.e. one-sided 0.0125 for each hypothesis.

The estimates of exclusion rates and standard deviation are based on the data from previous qHPV vaccine and 9vHPV vaccine studies.

The overall power to establish the non-inferiority of the dual-primary endpoints: (1) cLIA GMTs in 9-19 yr vs. 20-26 yr; and (2) cLIA seroconversion percentages in 27-45yr vs. 20-26yr will be at least 99.1% and 92.9% respectively, at a level of 0.0125.

The overall power to establish the non-inferiority of the secondary endpoints: (1) cLIA seroconversion percentages in 9-19yr vs. 20-26yr and (2) cLIA GMTs in 9-15yr vs. 20-26y will be at least 98.4% and 95.8% respectively, at a level of 0.0125.

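### Section 9.8 controls type I error but leaves 0.0125 unused after an H2 win and 0.0125 unused after H1, H3 and H4 are all won; two alpha transfers would recover power at little cost

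*Combined protocol and SAP*

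**What the plan says.** Section 9.8 states that the "Bonferroni method is used to control overall one-sided type I error at level of 0.025", and that "Each of the dual-primary hypotheses has a 0.0125 one-sided type I error". The secondary hypotheses hang on H1 only: "if H1 wins H3 (seroconversion percentages, 9-19yr vs. 20-26yr) will then be tested", and H4 follows H3. The level is the same at every step, and a failure ends the sequence: "Each one will be tested at a level of 0.0125. If anyone failed to reject null the subsequent ones would not be tested". Within a hypothesis no further adjustment is needed, since "success is required on all 9 HPV types for hypotheses testing GMT and seroconversion percentages". On the study as a whole: "The study would be successful if either H1 or H2 are met".

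No sentence moves alpha from H2 to the chain or from the chain to H2, and no reason is given for leaving it where it is. Figure 2 is missing from the copy used here, so this reading rests on the text, which fixes every level. The fixed split is carried into the two-sided 97.5% CI written into H1 to H4 (Sections 1.1 and 3.1), Sections 9.1, 9.6.1 and 9.9.1, and Table 3.

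Section 9.9.1 gives overall powers of 99.1% (H1) and 92.9% (H2), and above 0.999 for study success. For the secondary comparisons it gives, for H3 and then H4, "cLIA GMTs in 9-15yr vs. 20-26y will be at least 98.4% and 95.8% respectively, at a level of 0.0125".

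**The concern.** Sections 2.1 and 4.1 say that the Stage I results are meant to support two extensions of the indication, to 9-15 and to 27-45 years. The 27-45 comparison is H2, which has the lowest stated power of the four. H4 is the only confirmatory test in the 9-15 group itself, and it comes last in its sequence. Under Section 9.8, H2 is still tested at 0.0125 when the whole younger-age chain has been won, and the chain is still tested at 0.0125 when H2 has been won. In both cases alpha that could be used without raising the family-wise rate is left idle.

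A second, smaller point concerns how the powers are reported. H4 can be claimed only if H1 and H3 both pass, yet the powers quoted for H3 and H4 take no account of that gate.

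**Working it through.** **Inputs (Section 9.9.1, Tables 6 to 8).** SD of log titer 1.2; GMT-ratio margin 0.67; true ratio 1; seroconversion 98% in every group; margin -5 points. Effective sizes are 586/455 (H1, H3), 391/455 (H4) and 455/455 (H2). Per-type powers are multiplied over nine types.

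**1. Reproduce the plan at one-sided 0.0125 (z = 2.2414).**
- GMT: SE = 1.2 × √(1/n1 + 1/n2), shift = -ln(0.67) = 0.4005. H1: SE 0.0750, shift/SE 5.341. H4: SE 0.0828, shift/SE 4.840. Noncentral-t power per type is 0.99901 (H1) and 0.99521 (H4); to the ninth power, 0.9911 and 0.9577.
- Seroconversion (asymptotic Miettinen-Nurminen): power = Φ[(0.05 - z·s0)/s1], with s0 from the estimates restricted to a difference of -0.05 and s1 from 98% in both groups. H2: s0 = 0.01235, s1 = 0.00928, Φ(2.404) = 0.99189; ninth power 0.9293. H3: s0 = 0.01094, s1 = 0.00875, Φ(2.912) = 0.99820; ninth power 0.9839.

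All four match the stated 0.991, 0.958, 0.929 and 0.984.

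**2. Same formulas at one-sided 0.025 (z = 1.9600).** H1 0.9967, H2 0.9757, H3 0.9951, H4 0.9819.

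**3. Validity of the transfers.** Each hypothesis is an all-nine-types test at its own level. Start with 0.0125 on H1 and 0.0125 on H2, and route alpha H1 to H3, H3 to H4, H4 to H2, and H2 to the first unrejected hypothesis in the chain. This is a Bonferroni-based graphical procedure, so the family-wise rate stays at 0.025. It rejects everything that the current rule rejects. Nothing is taken from H3 or H4, because chain alpha reaches H2 only after H4 is won.

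**4. Power with transfers, plan's method, hypotheses treated as independent.**
- Chain H1, H3, H4 at 0.0125: 0.9911 × 0.9839 × 0.9577 = 0.934. At 0.025: 0.9967 × 0.9951 × 0.9819 = 0.974.
- H2: 0.9293 + (0.9757 - 0.9293) × 0.934 = 0.973.
- H4 reached and won: 0.934 + (0.974 - 0.934) × 0.9293 = 0.971.
- All four: from 0.934 × 0.9293 = 0.868 to 0.9293 × 0.974 + (0.9757 - 0.9293) × 0.934 = 0.948.

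**5. Check by simulation.** 40,000 trials, shared 20-26 group, Miettinen-Nurminen test, types independent of one another, titer and seroconversion independent of each other:

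| | Plan's method: now → with transfers | Simulation: now → with transfers |
|---|---|---|
| H2 | 0.929 → 0.973 | 0.948 → 0.981 |
| H4 reached and won | 0.934 → 0.971 | 0.949 → 0.977 |
| All four | 0.868 → 0.948 | 0.900 → 0.961 |

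Simulated H1 moves from 0.992 to 0.997, and H3 reached and won from 0.983 to 0.994.

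**6. Correlated types.** The documents give no correlation between types. Assuming equal correlation among the nine test statistics and starting from exact per-type powers, H2 goes from 0.961 to 0.986 at a correlation of 0.5 and from 0.971 to 0.989 at 0.7. These compare 0.0125 with the full 0.025, so they are ceilings on the gain (+2.5 and +1.8 points).

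**7. If the H2 assumptions slip.** These scenarios are assumed (exact test, independent types). With 97.5% against 98%, H2 has power 0.725 at 0.0125 and 0.879 at 0.025. With 97% in both groups, 0.736 and 0.880. H2 gets the higher level only when the chain is won.

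**8. Gated powers as designed.** By multiplication, H3 is 0.991 × 0.984 = 0.975 and H4 is 0.991 × 0.984 × 0.958 = 0.934. Simulation, which keeps the overlap of H1 and H4, gives 0.983 and 0.949.

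**9. Study success.** 1 - (1 - 0.991)(1 - 0.929) = 0.9994, agreeing with the stated >0.999. Transfers cannot change it: alpha moves only after H1 or H2 has already been won.

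**The case against.** The strongest reply is that nothing here is wrong. Type I error is controlled, each stated power fits the level used, every hypothesis has at least 92.9% marginal power, and study success cannot improve. Bonferroni with a fixed sequence is a legitimate choice. All of that stands.

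A reader might infer that half the alpha is lost after any win. Section 9.8 does not support that, because H1's 0.0125 is reused for H3 and H4. Nor does the fixed split bring no benefit. It gives one pre-set 97.5% CI per claim and keeps the younger-age and older-age decisions separate, although the documents do not offer this as their reason.

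The gains also depend on the method. The asymptotic formula understates H2 power (0.929 against 0.948 by exact enumeration) and so enlarges the apparent gain. All nine titers come from one multiplexed assay of the same serum (Section 8.2.2), so positive correlation is plausible and would shrink the gain further.

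It is tempting to say that the 9-15 extension requires H4. The documents do not say so. Section 4.2.1.1 makes titer in 9-19 years the primary endpoint and cites regulatory precedent. It is also tempting to call the H3 and H4 powers wrong. They are correct as powers of each comparison at 0.0125, and only the gate is missing.

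Finally, the study is open-label with an unblinded sponsor (Sections 6.3.2 and 9.2). A late move to a 95% CI would look data-driven. That objection stands and sets the deadline for the change.

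**Conclusion.** The point holds as an efficiency improvement. Alpha is idle in exactly two situations, after an H2 win and after H1, H3 and H4 are all won, and both can be used at no cost to the family-wise rate. The gain is about 2 to 4 points on H2, about 3 to 4 points on H4 reached through the chain, and about 6 to 8 points on winning all four. It is zero for study success.

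The upper ends come from the plan's asymptotic method, the lower ends for H4 and all four from the simulation, and the lower end for H2 from correlated types. The H4 and all-four figures assume independent types, so their gains too would be smaller under positive correlation. The gain on H2 would be larger if seroconversion fell slightly short of the assumed 98%.

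The reporting point is modest: gated power is about 97.5 to 98.3% for H3 against the stated 98.4%, and about 93 to 95% for H4 against 95.8%.

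**What to change.** In Section 9.8, keep the 0.0125/0.0125 start and the H1, H3, H4 order, and add two rules:

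- If H2 is rejected, its 0.0125 passes to the first unrejected hypothesis in the chain and then along it, so that the hypothesis is tested at 0.025 in total.
- If H1, H3 and H4 are all rejected, their 0.0125 passes to H2.

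A hypothesis holding 0.025 is judged by the two-sided 95% CI, otherwise by the 97.5% CI. Change the CI wording to match in H1 to H4 (Sections 1.1 and 3.1), Sections 9.1, 9.6.1 and 9.9.1, and Table 3, and align Figure 2. Tabulate both intervals.

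In Section 9.9.1, label 98.4% and 95.8% as marginal powers at 0.0125 and add the gated values.

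The cost is a protocol amendment, which Section 9 already requires for changes to H1-H4 methods, and a CI level that depends on the path taken. Section 9 allows such changes up to database lock, but that is too late here: this one must be in force before any post-Dose 3 serology is available to the sponsor. If such results already exist, leave the testing rule alone and make only the power restatement.
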